1.6 Study Rationale, Benefits and Risks

This study is designed to evaluate the efficacy of two geko™ daily treatment durations in conjunction with Standard Care (SC), consisting of multilayer, multicomponent compression therapy intended for the treatment of VLU, compared with each other and to that of SC alone in participants with VLUs. geko™ has been shown to facilitate wound healing in earlier studies (See Section 1.5 Summary of prior clinical studies) and patients receiving the geko™ 6h or 12h daily in addition to SC may experience faster wound healing as well as greater pain reduction than patients treated with SC alone. We believe that treatment with geko™ will in conjunction with SC potentially lead to faster healing and re-epithelialisation than treatment with SC alone for patients with VLU.

A potential risk for participants randomised to the geko™ daily treatments is the possibility of eczema at the application site. This, however, is unlikely based on previous experience with geko™ (20). Potential adverse events for all research participants in this study are intrinsic to the nature of VLUs, including but not limited to: pain and infection at the wound site, and maceration of the surrounding skin.

Not all patients may respond to the geko™ stimulus. Therefore, patients with no involuntary movement of the lower leg/foot at the maximum tolerable device setting will be excluded from the study.

2 Study Objective

The objective of this study is to compare the efficacy of a daily geko™ device treatment durations of 12 hours, in conjunction with SC, to SC alone, in patients with venous leg ulcers.

2.1 Efficacy Endpoints

2.1.1 Primary Efficacy Endpoint

The primary efficacy endpoint is linear healing rate (LHR) from TV1 to EOT as compared with LHR from RV1 to TV1. LHR will be calculated by linear regression of the 4 measurements in each phase, with linear wound edge advance being based on the change with respect to time of wound area divided by perimeter, according to Vidal's method (22) [Each participant will be used as his/her own control, i.e. a participant's healing trajectory before introduction of treatment will be compared to his/her healing trajectory after introduction of treatment. Wound area and perimeter will be measured by a blinded independent wound expert using digital images taken at baseline (RV1), first treatment visit (TV1) and at EOT.

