Indication for Use: Indicated for use as an adjunct to Standard Care (SC) in the treatment of Venous Leg Ulcers (VLUs)	
Objective: The objective of this study is to compare the efficacy of a daily geko™ device treatment duration of 12 hours, in conjunction with SC, to SC alone, in patients with venous leg ulcers.	
Endpoints: Primary Efficacy The primary efficacy endpoint is linear healing rate (LHR) of the study ulcer from first Treatment Phase visit (TV1) to the End of Treatment (EOT) as compared with LHR from first Run-in Phase visit (RV1) to TV1. 
• EOT is defined as Treatment Phase visit 5 (TV5), withdrawal or that Treatment Phase visit at which 100% re-epithelialisation without drainage is first determined by the Principal Investigator (PI) or designee, whichever comes first. Each participant will be used as his/her own control. Wound area will be measured by a blinded independent wound expert using digital images taken at RV1, TV1 and at EOT. “Healing” of the study ulcer is determined by the PI or designee. “Healing” is defined as 100% re-epithelialised without drainage as confirmed at the Healing Confirmation visit (HCV).	

Name of Sponsor/Company: Firstkind Ltd, [name]	
Name of Study Product: geko™ neuromuscular stimulator	
Comparator Product: Multilayer, multicomponent compression therapy intended for the treatment of VLU (Standard Care)	
Protocol Number: FSK-VLU- 004	Indication: Venous Leg Ulcers (VLUs)

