4.3 Healing Confirmation

Only those subjects whose study ulcer is 100% re-epithelialised without drainage as determined by the PI or designee during a TV, will be scheduled for a Healing Confirmation Visit (HCV). The HCV is to be scheduled a minimum of 7 days after the first determination of re-epithelialisation.

During the HCV perform the activities in the following order:

- Administer the CWIS and EQ-5D-5L questionnaires in the participant's primary language.

- Administer the study ulcer pain VAS assessment.
- Check for any changes in the participant's health and update the AE or SAE CRF pages if applicable.
- Assess concomitant medications.
- Assess compression bandaging (See Section 9.8).
- Assess study ulcer healing (to be performed by treating PI or designee).

If the study ulcer remains 100% re-epithelialised without drainage:

- Obtain a digital image of the study ulcer site.
- Provide appropriate follow-up therapy for the participant and the healed ulcer and exit the participant from the study.
- Complete the remaining applicable visit (TV5) procedures.

If the study ulcer remains 100% re-epithelialised without drainage at the HCV, the date of healing for the purpose of study results will be the date 100% re-epithelialisation without drainage was first determined by the PI or designee.

If the study ulcer is NOT 100% re-epithelialised without drainage:

- Complete the remaining visit (TV5) procedures.
- Check for signs of clinical infection.
- Clean the study ulcer.
- Obtain a digital image of the study ulcer.
- Provide appropriate follow-up therapy for the participant and the non-healed ulcer and exit the participant from the study.

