10.7 Description of Study Endpoints

10.7.1 Primary Efficacy Endpoint

The primary efficacy endpoint for the study is LHR from TV1 to EOT as compared with LHR from RV1 to TV1. LHRs will be measured by a blinded wound expert using digital images at RV1, TV1, EOT, and at HCV if scheduled.

Each participant will be used as his/her own control, i.e. a participant's healing trajectory before commencement of treatment will be compared to his/her healing trajectory after introduction of treatment.

Since significant non-homogeneity may be expected in VLU participants and their respective healing trajectories, a pre-treatment run-in phase will be used to allow each participant to be used as his/her own control, i.e. a participant's healing trajectory before introduction of treatment will be compared to his/her healing trajectory after introduction of treatment. This allows an intra-group pair-wise comparison to evaluate the efficacy of each treatment regimen.

Additionally, for each participant, it enables generation of a treatment healing rate normalised relative to an initial healing rate. Inter-group (albeit un-paired) comparisons based on this normalised value are likely to be more sensitive than comparison of raw healing rates.

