10.12.1 Efficacy Analyses

Primary Endpoint: The primary efficacy endpoint is linear healing rate (LHR) from TV1 to EOT as compared with LHR from RV1 to TV1. LHRs will be measured by a blinded wound expert using digital images at RV1, TV1, and EOT.

Within treatment groups, treatment phase will be compared to run-in phase by paired non-parametric test (Wilcoxon signed rank). Effects will be compared between groups using non-paired non-parametric tests (Mann-Whitney).

Secondary Endpoints:

Weekly LHR shall be compared as above.

EOT healing status between groups shall be compared by Mann-Whitney U test on the PWAT scores. Weekly LHR can be tested using the same method (and same wording) as final LHR. Incidence of healing shall be compared between groups using Fisher's exact test.

Intra-group pain reduction measured on a visual analogue scale (VAS) will be analysed using paired t-test.

Inter group differences in time to clinically significant reduction in VAS shall be tested using Mann-Whitney u-test.

Intra-group changes to both Quality of Life (QoL) instruments in the study (CWIS and EQ-5D-5L) shall be tested using Wilcoxon signed rank test.

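### The primary linear healing rate is defined on contradictory sets of visits, so no single calculation follows from the protocol as written

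*Combined protocol and SAP*

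**What the plan says.** Section 2.1.1 sets the endpoint as the linear healing rate (LHR) from TV1 to end of treatment (EOT), compared with the LHR from RV1 to TV1. On calculation it says "LHR will be calculated by linear regression of the 4 measurements in each phase". It cites a published method for the quantity itself, which it describes as "linear wound edge advance being based on the change with respect to time of wound area divided by perimeter". It then says that area and perimeter are read from "digital images taken at baseline (RV1), first treatment visit (TV1) and at EOT".

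Other current text on the same endpoint:

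- Synopsis, primary efficacy: "Wound area will be measured by a blinded independent wound expert using digital images taken at RV1, TV1 and at EOT". Perimeter is not mentioned.
- Section 10.7.1: "LHRs will be measured by a blinded wound expert using digital images at RV1, TV1, EOT, and at HCV if scheduled".
- Section 10.12.1: "LHRs will be measured by a blinded wound expert using digital images at RV1, TV1, and EOT".
- Synopsis, Table 1, Table 2 and 9.9.9: visits RV1 to RV5 and TV1 to TV5, with RV5 and TV1 the same visit and an image at each weekly visit.
- Synopsis, definition of EOT: the earliest of TV5, "withdrawal or that Treatment Phase visit at which 100% re-epithelialisation without drainage is first determined".
- Section 4.3: "The HCV is to be scheduled a minimum of 7 days after the first determination of re-epithelialisation".

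Sections 10.1 and 10.12 leave detail to a separate SAP, to be approved before database lock. Section 10.5.2 already reports an interim run-in versus treatment difference for geko 12h of 0.58 mm/week, with a standard deviation of 0.97 mm/week.

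**The concern.** A regression on four values per phase cannot be run on two. Nor does four match the schedule, which supplies five time points per phase when TV1 is counted in both. The text does not say which four visits are meant, or whether TV1 belongs to one phase or to both. When EOT falls at TV2 or TV3, the treatment phase holds only two or three images, so four is impossible. Section 10.10.1 admits such participants to the primary analysis population, and no rule covers short series. The HCV image in 10.7.1 comes at least 7 days after closure, outside that section's own TV1-to-EOT interval.

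Two competent analysts could therefore compute different primary values for the same participant, each with support in the text. The choice would also be made after the direction and size of the interim result in the active arm are known, which is when a primary endpoint should no longer be open.

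**Working it through.** **1. The plan's own figure.** Inputs from 10.5.2: difference 0.58, SD 0.97 (read as the SD of the paired difference), 80% power, two-sided 0.05. The normal approximation gives ((1.960 + 0.842) × 0.97 / 0.58)² = 21.95, so 22. The exact paired t calculation (noncentral t) gives 80.1% power at n = 24 and 81.8% at n = 25. The stated 25 is within one of the exact answer. It also agrees with 24 / 0.955 = 25.1, the usual allowance under normality for the Wilcoxon test named in 10.12.1.

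**2. Time points per phase under each statement.**

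| Source | Run-in | Treatment |
|---|---|---|
| 2.1.1, regression sentence | 4 | 4 |
| 2.1.1, imaging sentence; Synopsis; 10.12.1 | 2 (RV1, TV1) | 2 (TV1, EOT) |
| 10.7.1 | 2 | 2, plus HCV after EOT |
| Visit schedule and 9.9.9 | 5 | 5, or fewer if EOT is before TV5 |

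**3. Precision under each visit set.** Assume weekly visits at weeks 0 to 8, TV1 at week 4, EOT at TV5, and independent errors of variance 1 per image. A least-squares slope gives the image at time t the weight (t − mean) / Sxx and has variance 1 / Sxx. If TV1 is used in both phases, its error enters the two slopes with opposite signs. The variance of the difference is then the sum of the two slope variances plus 2 × (run-in weight at TV1) × (size of the treatment weight at TV1).

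- Five per phase: Sxx = 10, TV1 weights ±0.2. Variance = 0.1 + 0.1 + 2 × 0.2 × 0.2 = 0.28.
- RV1/TV1/EOT: Sxx = 8, TV1 weights ±0.25. Variance = 0.125 + 0.125 + 2 × 0.25 × 0.25 = 0.375.
- Four per phase with both ends kept (nine combinations): 0.28 to 0.36.
- Four consecutive per phase: Sxx = 5. If TV1 is in at most one phase, 0.2 + 0.2 = 0.40. If TV1 is in both (RV2 to TV1 and TV1 to TV4), weights ±0.3 give 0.4 + 2 × 0.3 × 0.3 = 0.58.

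**4. Consequence for n.** Section 10.5.2 does not say which visit set gave 0.97. Let f be the share of 0.97² due to measurement error; the documents give no value, so 0.25 to 0.50 is assumed. Let r be the ratio of final to interim error variance. The SD becomes 0.97 × √(1 − f + f × r), and n is the exact paired t answer for 80% power.

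| Interim set → final set | r | f = 0.25 | f = 0.50 |
|---|---|---|---|
| Five images → RV1/TV1/EOT | 0.375 / 0.28 = 1.34 | SD 1.010, n = 26 | SD 1.049, n = 28 |
| RV1/TV1/EOT → five images | 0.28 / 0.375 = 0.75 | SD 0.939, n = 23 | SD 0.906, n = 22 |

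**The case against.** The best defence is that nothing is lost. Section 9.9.9 sends all images to the blinded expert, 2.1.2 already requires a blinded weekly LHR, and the SAP is to supply detail before lock. That is true, and it makes the repair cheap. But a SAP can only choose one version; it cannot satisfy sentences that conflict. A milder reading takes the four measurements as the four weekly changes between five visits. The text does not say this, and it would still conflict with the three-image lists.

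The HCV reference is largely settled by context: 10.7.1 limits the interval to TV1 to EOT, and 10.12.1 omits HCV. It needs deletion, no more. The leftover references to percentage area reduction (PAR) in 9.9.9 and 10.5 look unrevised, since 10.5.1 uses LHR and 10.5.2 reports mm/week.

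Three stronger readings are tempting and not supported:

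- That the formula itself is undefined. The equation is not printed, and the wording could mean the slope of area over perimeter or the change in area divided by a perimeter. The cited method may settle it. A material shift in the treatment-minus-run-in difference was found only when the RV1 perimeter was used as a fixed divisor in both phases, which no section mentions.
- That the poor precision after an early EOT measures this error. It arises under either visit set: 0.80 (weekly images) against 0.875 (RV1/TV1/EOT) at TV3, and 2.50 against 2.625 at TV2.
- That the sample size is wrong. It reproduces on its own inputs.

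**Conclusion.** The visit definition of the primary endpoint is wrong as written: section 2.1.1 contradicts itself, and the Synopsis, 10.7.1, 10.12.1 and the schedule do not resolve it. The error variance of the within-participant contrast ranges from 0.28 to 0.58 across the visit sets considered, given independent and equal error per image and a full treatment phase. The effect on sample size is modest. It is about 22 to 28 for a switch between five images and RV1/TV1/EOT, and that range rests on an assumed 25 to 50% error share and on an interim visit set that is not stated. A reader might infer that n = 25 is invalid or that data are missing. Neither follows, because 24 to 25 is reproduced and the weekly images are scheduled. The main harm is that a primary outcome remains open to choice after an interim result of 0.58 mm/week has been reported.

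**What to change.** Put one definition in the Synopsis, 2.1.1, 10.7.1 and 10.12.1 before the final blinded reading of images:

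1. LHR is the regression, on actual visit dates, of all weekly pre-debridement images from RV1 to TV1 inclusive (run-in) and from TV1 to EOT inclusive (treatment). The value is set to zero at closure, where area over perimeter would otherwise be 0/0.
2. Delete the four-measurement wording, the three-image lists and the HCV reference for LHR.
3. Use all available images, with a minimum of two per phase. Add a sensitivity analysis limited to participants with three or more treatment images.

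Alignment notes:

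- Print the equation of the cited method, including which perimeter it uses and how perimeter is handled when an ulcer splits (9.9.9 combines areas only).
- Replace the PAR wording in 9.9.9 and 10.5, and have perimeter read on every image used.
- State which version of LHR gave 0.58 and 0.97.

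Using all weekly images is one valid choice among several. It is preferred because it had the lowest variance of the sets checked (0.28, equalled only by one four-image choice) and matches the weekly secondary endpoint. The cost is protocol and SAP wording. Slightly more images enter the primary reading, but all are already scheduled and already needed for the weekly LHR. The interim figures need recomputing only if they came from a different version.

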2.1.2 Secondary Efficacy Endpoints

The secondary efficacy endpoints are:

- Weekly LHR measured by an independent blinded wound expert using digital images taken at each weekly visit until TV5, withdrawal or healing whichever comes sooner.
- Wound healing status at baseline and EOT assessed by an independent blinded wound expert using PWAT to evaluate digital images taken at RV1, TV1 and at withdrawal, healing or at the end of the Treatment Phase (TV5), whichever comes sooner.
- Incidence of healing at EOT, as determined by the Investigator

“Healing” of the study ulcer is determined by the PI or designee. “Healing” is defined as 100% re-epithelialised without drainage as confirmed at the Healing Confirmation visit (HCV).

2.1.3 Participant Reported Secondary Efficacy Endpoints

The participant reported secondary efficacy endpoints are:

Time from TV1 to clinically significant pain reduction measured using a Visual Analogue Scale (VAS) instrument. For the purpose of this protocol a clinically significant reduction of pain is a mean reduction of ≥ 20.65 mm or a mean decrease of $\geq 10\text{-}20\%$ in pain as measured on a 0-100 mm VAS (23; 24).

Time from TV1 to first instance of no study ulcer pain measured using VAS.

(No pain = < 5 mm on VAS when VAS scores: 0-4 mm = no pain; 5-44 mm = mild pain; 45-74 mm = moderate pain; and 75-100 mm = severe pain) (1).

Pain score at EOT measured using VAS

Change from TV1 in Quality of Life (QoL) at EOT, assessed using the Cardiff Wound Impact Schedule (CWIS)

Change from TV1 in QoL at EOT, assessed using EQ-5D-5L

Wound closure as reported by participants during the Follow-up Phase (FP1-FP3)

The two QoL instruments, the CWIS a wound specific QoL instrument, and the EQ-5D-5L, a standardised instrument for measuring generic health status, will be provided to the participants for completion at RV1, TV1 and at EOT. In case of withdrawal all attempts should be made to obtain final QOL assessments.

2.2 Safety assessment

Safety will be assessed based on incidence of adverse events (AEs), incidence of serious AEs (SAEs), incidence of study treatment related AEs, incidence of investigational device related AEs, ulcer infection, and incidence of pain in the ulcer site (sudden onset of pain or increase in pain during the study treatment).

3 Study Design

This study is designed as a prospective, multicentre, randomised, assessor blinded study designed to compare the efficacy including participant reported outcomes of two different gekoTM treatment durations in conjunction with SC, with each other and with SC alone, in the treatment of patients with venous leg ulcers. There will therefore be two arms in the study consisting of: 1) participants randomised to receiving SC only; 2) participants randomised to receiving SC, and gekoTM 12 hours daily.

The standard care therapy in this study is multilayer, multicomponent compression therapy intended for the treatment of VLU. A non-adherent (NA) wound contact dressing and/or an absorbent dressing may be used if required, at the Investigator's discretion in addition to SC. All dressing use and reason for dressing use will be recorded.

Multiple multilayer, multicomponent compression bandaging systems delivering levels of compression and with clinical data to support their use are commercially available. The compression bandaging system of choice based on local best practice will be used. Moreover, this will prevent any problems around consistency of method of application of compression.

The study will be a multinational, multicentre study with study centres in the UK and Europe

The study will have three phases: a four-week Run-in Phase, a four-week Treatment Phase and a twelve-week follow-up phase. A schematic picture of the study flow is provided below in Figure 1.

[figure not shown]

Figure 1: Study Schedule

At or up to 21 days before the first Run-in Phase Visit (RV1), the Investigator or suitably qualified designee will, prior to the performance of any protocol-specific procedure, obtain written informed consent from the patient.

During the Run-in Phase participants will be evaluated on a weekly basis. Efficacy evaluations each week will include Investigator assessment of wound healing and measurements of ulcer size using digital images. For the purpose of this study, healing is defined as 100% re-epithelialisation without drainage confirmed at the Healing Confirmation visit (HCV). The compression bandaging system of choice based on local best practice in the study centre in question will be used.

The results of the four-week Run-in Phase during which only SC will be used as treatment, will provide an SC only healing trajectory (LHR curve) (22) for each of the participants and each participant will serve as his/her own control.

At RV1, the Investigator will assess and confirm the patient's eligibility and select the study ulcer. Each participant will have only one VLU selected as the study ulcer. In the situation where a participant has more than one VLU at the RV1 visit, the Investigator will select the largest VLU that meets the eligibility criteria of the protocol as the study ulcer. If other ulcerations are present on the same leg they should be more than 2 cm apart from the study ulcer.

At the first Treatment Phase visit (TV1), once the Investigator has confirmed the participant's continued eligibility, randomisation and assignment to study treatment will take place.

The total maximum study duration is nine weeks, followed up by twelve weeks Follow-up Phase. All participants remaining in the study at the final Treatment Phase visit, TV5, will complete study visits unless they present with 100% re-epithelialisation without drainage as determined by the PI or designee, in which case they will be scheduled for a Healing Confirmation Visit (HCV) in a minimum of 7 days. All participants attending a HCV will complete study visits at this visit regardless if healing is confirmed or not.

3.1 Study Population

3.1.1 Number of Participants

A total of 60 patients will be randomised into the study

3.1.2 Inclusion Criteria

The inclusion criteria of the study are:

1. Male or female aged ≥ 18 years and able to provide written informed consent.
2. Intact healthy skin at the site of gekoTM device application.
3. Patients who have a chronic venous leg ulcer determined to be due to underlying venous disease following evaluation in a multidisciplinary clinic setting or by a vascular surgeon, GP or Nurse specialist.
4. *A VLU of approximately $\geq 3\text{cm}^2$ and $\leq 39\text{ cm}^2$ at study enrolment i.e. Run In Phase Visit 1 (RVI).* The largest ulcer within the given size range will be designated the study

ulcer and the only one included in the study. If other ulcerations are present on the same leg they have to be more than 2 cm apart if they are separate wounds.

5. Study ulcer (current episode of ulceration in case of ulcer recurrence) has been present for at least 6 weeks but no more than 5 years prior to study entry.
6. Ankle-Brachial Pressure Index (ABPI) of 0.75-1.24 inclusive measured at study entry or within 8 weeks of study entry
7. No active index wound infection for a minimum of 48 hours prior to study entry (i.e. RV1).
8. No systemic antimicrobial treatment for a minimum of seven days prior to study entry prescribed for index wound infection (i.e. RV1).
9. Patient understands and is willing to participate in the study and is able to comply with study procedures and visits.

